There is much still to be learned in the understanding of bleeding and thrombosis in the perioperative period. Perioperative events can lead to a great deal of variability in pro- and anti-thrombotic hemostatic factor levels.²⁹ Therefore, the propensity for thrombosis and bleeding in individual patients is frequently unpredictable and, can change substantially over time. Opportunity for discovery is heightened for patients with LVADs, given the dearth of rigorous investigations and the unique features of the human-machine interface. With the recent reports of increasing suspected and confirmed devastating (LVAD) pump thrombosis in the early post-implant period⁴, analyses of treatment-related factors such as the method of monitoring anticoagulation are urgently needed. Recent studies in patients with LVADs have correlated factors such as international normalized ratio (INR) in the outpatient setting³⁰, medication use³¹, and elevated systolic blood pressure³² to pump thrombosis and stroke. However, the impact of monitoring IV UFH therapy with aPTT or anti-Xa in the perioperative period on pump thrombosis, stroke and bleeding remains unknown. The early risk for both bleeding and thrombosis in patients with LVADs underlines the urgency of resolving how best to monitor and achieve appropriate anticoagulation with heparin. Given the ongoing challenges with these competing complications, studying the problem in earnest, while taking into consideration perioperative events, is crucial. Clarifying which of these two monitoring approaches is superior will facilitate safer and more effective anticoagulation with heparin in patients with LVADs.

B Study Objectives

Primary Outcome:

Demonstrate the feasibility and success of implementing nomograms for heparin administration based on both aPTT measurement and anti-factor Xa activity.

Feasibility will be determined by: 1) Questionnaires evaluating the practicality and acceptability of the nomograms 2) The percentage of correct dosing adjustments made by the nursing team required to achieve first therapeutic anticoagulation according to the specified directions provided.

Success will be determined by 1) number of dosing changes required to achieve first therapeutic anticoagulation 2) time (in hours) until achievement of first therapeutic anticoagulation 3) percentage of time therapeutic anticoagulation remains after it is achieved

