“Therapeutic anticoagulation” is defined as two consecutive monitoring values within the goal range, according to assigned monitoring assay. (either two consecutive aPTT values within 60-94 seconds or two consecutive anti-Xa values within 0.3-0.7 IU/ml)

Secondary Outcomes:

Explore heparin dosing and the concordance between the aPTT and anti-factor Xa activity in this patient population.

“Concordance” is defined when simultaneously drawn aPTT values and anti-Xas values are within the goal range (aPTT within 60-94 seconds and anti-Xa within 0.3-0.7 IU/ml).

Explore clinical outcomes including pump thrombosis, gastrointestinal bleeding, neurological events such as stroke, and major bleeding in this patient population.

C Study Design

Study setting and design

VAD AntiX feasibility study will take place at Barnes-Jewish Hospital, an academic hospital in affiliation with Washington University Medical Center located in the United States. This trial has been designed in accordance with the SPIRIT (Standard Protocol Items: Recommendations for Interventional Trials) checklist³³. The VAD AntiX feasibility study will be a stratified randomized, trial with one specific aim: (1) Demonstrate the feasibility of implementing nomograms for heparin administration based on aPTT measurement as well as anti-Xa activity. This feasibility trial will be the foundation for a larger pilot trial and subsequent comparative effectiveness trial that will seek to determine the optimal monitoring method of IV UFH in the perioperative period for LVAD patients.

A heparin nomogram is a tool or table used to standardized heparin administration and dosing when heparin is administered as a continuous infusion. Dosing adjustments are prescribed in the table based on the laboratory results.

Subject Selection

All patients 18 and older undergoing HeartMate II®, HeartMate III® or HeartWare®, LVAD implantation at Barnes-Jewish Hospital, St. Louis, Missouri, USA will be eligible for enrollment in this study. This hospital is an academic medical center affiliated with Washington University School of Medicine. Patients will be recruited preoperatively and will provide written informed consent. Any patient who is unable to receive heparin [e.g. patients with heparin-induced thrombocytopenia (HIT)] or an anaphylactic allergy to heparin] will be excluded. Patients who develop HIT during the course of the study will remain enrolled and be included in the intention-to-treat analysis.

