weight-based nursing driven heparin nomogram starting at 12 units/kilogram/hour without a bolus. Patients randomized to aPTT monitoring will follow our institution's current nursing-driven aPTT nomogram and the patients randomized to anti-Xa monitoring will follow a nursing-driven anti-Xa nomogram. Each nomogram has instructions regarding scheduled assay lab draws that nurses will follow. Regardless of group allocation, while IV UFH is administered according to one of the two nomograms, both the aPTT and the anti-Xa activity will be determined at specified time points, although clinicians will only receive the information according to group assignment. Clinicians will be instructed not to deviate from the randomized monitoring protocol. All relevant concomitant care, interventions, and laboratory draws will be at the discretion of the ICU and surgical teams as part of routine postoperative care.

Randomization and Design:

Following LVAD implantation, subjects will be randomized via computer-generated randomization by the study coordinator. Patient randomization will be stratified by LVAD type with HeartMate II®, HeartMate III®, and HeartWare® patients being randomized to the 2 nomograms separately by the assigned study coordinator. Randomization will take place within twelve hours after arrival to the ICU and be subsequent to monitoring and management of heparin anticoagulation with either an aPTT or anti-factor Xa based nomogram.

Subjects in this study will be offered the opportunity to participate in the Systematic Assessment and Targeted Improvement of Services Following Yearlong Surgical Outcomes Surveys (SATISFY-SOS #201203008).

aPTT and anti-Xa Nursing Driven IV UFH Nomograms

aPTT Result	Bolus Dose	Infusion Change
aPTT less than 40 seconds	None	Increase 3 units/kg/hour
aPTT 40-50 seconds	None	Increase 2 units/kg/hour
aPTT 51-59 seconds	None	Increase 1 unit/kg/hour
aPTT 60-94 seconds	None	No change
aPTT 95-104 seconds	None	Decrease 1 unit/kg/hour
aPTT 105-114 seconds	Hold infusion for 30 minutes	Decrease 2 units/kg/hour
aPTT greater than 114 seconds	Hold infusion for 1 hour	Decrease 3 units/kg/hour
Draw STAT aPTT 6 hours after each rate change. Once two consecutive aPTT's are therapeutic (60-94 seconds), then draw aPTT every am. Draw CBC Express every 72 hours until heparin is discontinued.		

Anti-Xa Result	Bolus Dose	Infusion Change
Anti-Xa less than 0.2 IU/mL	None	Increase 3 units/kg/hour
Anti-Xa 0.2-0.29 IU/mL	None	Increase 2 units/kg/hour

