Anti-Xa 0.3-0.7 IU/mL	None	No change
Anti-Xa 0.71-0.80 IU/mL	None	Decrease 1 unit/kg/hour
Anti-Xa 0.81-0.99 IU/mL	Hold infusion for 30 minutes	Decrease 2 units/kg/hour
Anti-Xa greater than 0.99 IU/mL	Hold infusion for 1 hour	Decrease 3 units/kg/hour

Draw STAT anti-Xa 6 hours each rate change.
Once two consecutive anti-Xa's are therapeutic (0.3-0.7 IU/mL), then draw anti-Xa every am.
Draw CBC Express every 72 hours until heparin is discontinued.

Duration of Study:

Patients will be followed for 14 days of heparin therapy or until heparin has been discontinued (e.g. changed to bivalirudin for anticoagulation or completed a transition to warfarin) if sooner than 14 days. If the patient has not received any IV heparin for 5 consecutive days they will be considered to have failed anticoagulation and the reason noted by the clinical team for discontinuation will be recorded.

The requirement for clinical team training and feedback:

A necessary first step in embarking on this feasibility trial is to train the clinical staff in the use of algorithms for IV UFH administration postoperatively in patients following implantation of the LVAD. It is important first to show that nomograms are practical such that clinicians can easily follow them, and second that by following the nomograms the target parameters are achieved. The collaborators in this study represent the key stakeholders responsible for the management of patients with LVADs in the postoperative period. As such, there is commitment from medical, nursing and pharmacy leadership to manage heparin administration based on either the current aPTT based or the new anti-Xa based nomogram (Table 2). During the feasibility phase, all the medical and nursing staff will undergo structured training in the rationale behind and implementation of the nomograms. Structured training will take place through formal physician and nursing in-services provided by our clinical nurse specialist and clinical pharmacist specialist. The training will include background information, practical advice, mock scenarios, trouble shooting and safety tips. To assess impact, questionnaires for the nurses taking care of the study patients will be handed out by the research team on each nursing shift. The research team will collect the completed forms for input into the database.

Risks and mitigation efforts:

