aPTT monitoring group: While on fixed-dose heparin (750 units/hr), an aPTT and an anti-Xa will be sent every 6 hours from the same tube (2.7 ml of blood in a light blue top tube). The tube will be sent and processed via standard procedure for the aPTT assay to which the patient is randomized. A paper requisition form and an assigned study ID number will accompany the tube with an order for an anti-Xa that will result in a research profile blinded to the clinical team, but available to the research team. This will be the process for all the subsequent aPTT/anti-Xa lab draws in the aPTT monitoring group. When the clinical team decides to start weight-based heparin dosing, the aPTT heparin nomogram order bundle will be ordered as per standard of care. The process noted above for lab draws and paper requisition forms will apply to the weight-based heparin nomogram as well. The aPTT and anti-Xa will be drawn every 6 hours until two values are in the therapeutic range. Once two values are within the therapeutic range, they will be drawn every 24 hours. All timed lab draws are current standard of care for patients being monitoring on heparin nomograms at BJH.

anti-Xa monitoring group: While on fixed-dose heparin (750 units/hr), an anti-Xa and an aPTT will sent every 6 hours from one tube (2.7 ml of blood in a light blue top tube). Monitoring heparin therapy with this frequency is current standard of care. The tube will be sent and processed via standard procedure for the anti-Xa assay to which the patient is randomized. A paper requisition form and an assigned study ID number will accompany the tube with an order for an aPTT that will result in a research profile blinded to the clinical team, but available to the research team. This will be the process for all the subsequent aPTT/anti-Xa lab draws in the anti-Xa monitoring group. When the clinical team decides to start weight-based heparin dosing (per standard of care), the anti-Xa heparin nomogram order bundle will be ordered. The process noted above for lab draws and paper requisition forms, will apply to the weight-based heparin nomogram

as well. The aPTT and anti-Xa will be drawn every 6 hours until two values are in the therapeutic range. Once two values are within the therapeutic range, they will be drawn every 24 hours. All timed lab draws are current standard of care for patients being monitoring on heparin nomograms at BJH.

Outcomes data

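### Section D slows blood draws to 24-hourly after two in-range values, while the nomograms and the endpoint require two consecutive ones, so sampling can slow before the endpoint is reached

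*Combined protocol and SAP*

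**What the plan says.** Section D (Nomogram intervention procedure) states for each arm: "The aPTT and anti-Xa will be drawn every 6 hours until two values are in the therapeutic range". It continues: "Once two values are within the therapeutic range, they will be drawn every 24 hours". It does not say that the two values must be consecutive, or on which of the two assays they must fall.

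The nomogram tables in Section C set a different switch. For aPTT: "Once two consecutive aPTT's are therapeutic (60-94 seconds), then draw aPTT every am". For anti-Xa: "Once two consecutive anti-Xa's are therapeutic (0.3-0.7 IU/mL), then draw anti-Xa every am". The aPTT table also says "Draw STAT aPTT 6 hours after each rate change", and the anti-Xa table has a matching instruction.

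Section B says that therapeutic anticoagulation "is defined as two consecutive monitoring values within the goal range, according to assigned monitoring assay". Under the Primary Outcome it lists "time (in hours) until achievement of first therapeutic anticoagulation" as one of three success measures. Section E compares that time between arms with a t-test or a Mann-Whitney U test.

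**The concern.** The time at which the endpoint is recorded depends on when blood is drawn. If sampling slows on a weaker condition than the one that defines the endpoint, a patient can be moved to daily draws before the endpoint is met. The confirming value is then seen up to 18 h later (24 − 6) for reasons unrelated to heparin control. Two patients with the same results could have different recorded times, depending on which section the staff applied. In a trial of 20 patients, a few such cases would be enough to shift the summary of this measure.

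**Working it through.** The plan gives no sample-size or timing calculation to reproduce. The check has three steps.

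**1. The rules side by side**

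| Section | Condition | What follows |
|---|---|---|
| B, definition | two consecutive in range, assigned assay | endpoint met |
| C, both nomograms | two consecutive in range, that nomogram's assay | a draw each morning |
| D, both arms | two in range | a draw every 24 h |

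The B and C conditions are the same event, so under those rules sampling cannot slow before the endpoint. The D condition can be met first.

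**2. The shortest sequence that separates them: in, out, in, in (hours from first draw)**

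- 0 h: in range.
- 6 h: out of range; the rate changes and a redraw follows at 6 h.
- 12 h: in range. This is the second in-range value but not a consecutive one. Section D's switch is met; the endpoint is not.
- Next draw: 12 + 6 = 18 h under the consecutive rule, or 12 + 24 = 36 h under Section D. If it is in range, the endpoint is recorded then.

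The difference is 18 h and needs no assumed probability. It takes the 24-hour interval literally; a morning draw, as the nomograms put it, could come sooner.

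**3. Illustrative size**

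Assumptions not in the documents: each draw is in range with chance p, draws are independent, the first draw comes at 6 h, and dose feedback is not modelled. The 6-hour redraw after an out-of-range value is kept throughout.

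- *Share affected.* The value after the first in-range one is also in range with chance p, and then the rules agree. Otherwise Section D's switch comes first, so the share is 1 − p. With lag-1 correlation 0.3 it is 0.7(1 − p), which is 28% at p = 0.6.
- *Mean time, consecutive rule.* 6(1 + p)/p². At p = 0.6: 6 × 1.6/0.36 = 26.7 h. At p = 0.7: 6 × 1.7/0.49 = 20.8 h.
- *Added time.* After an early switch, each attempt to confirm an in-range value takes 24 h instead of 6 h, and 1/p attempts are needed on average. Affected patients gain 18/p h on average, and the mean over all patients rises by 18(1 − p)/p. At p = 0.6: 18 × 0.4/0.6 = 12.0 h. At p = 0.7: 18 × 0.3/0.7 = 7.7 h.

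| p | Share affected | Mean, consecutive rule | Mean, Section D read literally |
|---|---|---|---|
| 0.4 | 60% | 52.5 h | 79.5 h |
| 0.6 | 40% | 26.7 h | 38.7 h |
| 0.7 | 30% | 20.8 h | 28.5 h |
| 0.8 | 20% | 16.9 h | 21.4 h |

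A simulation of 20,000 patients per scenario gave increases of 11.7 h at p = 0.6 and 7.6 h at p = 0.7, in line with the formula. For p from 0.4 to 0.8 and correlation 0 or 0.3, the median change among affected patients was +18 h in every scenario. Their time was longer in 71–95%, unchanged in 3–8% and shorter in 2–21%. It can be shorter because a 24-hour gap may skip out-of-range values.

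**The case against.** The strongest reply is that the nomogram is what operates at the bedside. Section C (Interventions) says that nurses follow the draw instructions on the nomogram. Section D itself has the nomogram order bundle ordered and calls its timed draws standard care for patients on heparin nomograms. Section A envisages an anti-Xa nomogram with the same draw timing as the aPTT one, and staff are to be trained on both. On this reading Section D is a loose paraphrase, and sampling never slows early.

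Much of this stands, and the missing word may well be a drafting slip. It does not settle the matter, for two reasons. No section says which text prevails. And the nomograms do not give a complete schedule: they time a draw from each rate change, but an in-range result means no rate change, so they give no interval for the confirming draw. Only Section D supplies one, and Section D carries the weaker switch.

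A reader might infer three stronger points that the documents do not support.

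- *That a later rate change could go unchecked for a day.* Section D gives routine intervals and is silent on rate changes. It does not cancel the nomograms' 6-hour redraw, which has no exception once daily draws begin. Longer mean times that assume draws stay daily after an out-of-range value fail for the same reason.
- *That the plan favours one arm.* The Section D wording is the same in both. The added time does depend on how often values leave range, so an arm difference could be altered if the assays differ in that respect, but the plan gives no figures on this.
- *That percentage of time therapeutic is distorted to the same degree.* It is counted only after two consecutive in-range values, when both texts already give daily draws. The omission mainly shifts when that measure starts.

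**Conclusion.** The point holds as an inconsistency between sections that can distort one of the three success measures. It takes effect only where Section D is applied literally and a patient's first two in-range values are not consecutive. The usual effect is a longer recorded time, though not always. The 18 h shift in the traced sequence follows from the plan's own intervals. The shares and means rest on assumed values of p, independence and an exact 24-hour gap, and are illustrations only. The measure is one of several under the Primary Outcome, in an unpowered convenience sample of 20. This should be corrected before enrolment, but it does not threaten the trial.

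**What to change.** Reconcile the definition in Section B, the two nomogram tables in Section C and both arm descriptions in Section D, so that the switch in sampling and the endpoint definition use the same rule on the assigned assay. Have Section D cross-refer to the nomograms, including their draw after a rate change. State once the interval for the confirming draw after an in-range value, and whether the later draws are 24-hourly or each morning. Which schedule applies is for the sponsor to decide. The cost is wording in the protocol and the order bundles; sample size, assays and analysis are unchanged.

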Statistical Methodology	
Chi Square and descriptive statistics used for questionnaire responses.
 
Mann Whitney U test for dosing adjustments and time until first anticoagulation.
 
Students t test or Mann Whitney U for dosing changes required, time until therapeutic anticoagulation, and percentage of time therapeutic anticoagulated

	Concordance assessed with mixed effects model; repeated measures ANOVA and Turkey's test for multiple comparisons to analyze heparin administration. Clinical outcomes will be compared with a Chi square test. Intention to treat analysis will be used.
--	---

A Background and Rationale

Mechanical Circulatory Support

The prevalence of heart failure in the United States currently exceeds five million and continues to rise.¹ It remains the primary diagnosis in over one million hospitalizations annually, with an economic burden exceeding \$30 billion in the United States.² People with severe heart failure and symptoms at rest may be treated with mechanical circulatory support (MCS) pumps, such as a left ventricular assist device (LVAD). This pump is used as a long-term destination therapy or as a bridge to receiving a heart transplant. As the number of organ donors remains relatively fixed, and conventional medical therapies fail, MCS is increasingly utilized in this patient population with total implants approaching 2,500 per year.³

Complications of Mechanical Circulatory Support

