specialized in post-cardiothoracic surgery care noted 100% satisfaction with the utilization and implementation of our current weight-based heparin nomogram. All nurses noted that the nomogram was clear and easy to follow. Fifty-five (98.2%) nurses felt the current dosing provided in the nomogram is feasible and 53 (94.6%) stated that they follow the dosing and monitoring instructions exactly as they are written. A total of 49 (87.5%) noted that they seek clarification from a co-worker, pharmacist, nurse practitioner, or physician regarding the nomogram instructions. When asked about suggestions for improvement of the nomogram, the most common response was to create a nomogram that is more patient specific for surgical patients at a high risk of bleeding, such as patients with LVADs. These results suggest that implementing a second nomogram based on anti-Xa assay results, that mirrors the same instructions and timing of laboratory draws as the current aPTT-based nomogram, could also be feasible.

Potential Impact of VAD ANTIX

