For feasibility, questionnaires completed by the nursing staff evaluating the practicality and acceptability of the nomograms will be analyzed with descriptive statistics and compared between the two groups using a Chi square test. The percentage of correct dosing adjustments made by the nursing team required to achieve first therapeutic anticoagulation will be compared between the two groups using a Mann Whitney U test. For success, the number of dosing changes required to achieve first therapeutic

anticoagulation, the time (in hours) to achievement of first therapeutic anticoagulation, and the percentage time therapeutic anticoagulation remains after it is achieved will be compared between the two groups using a Student's t-test if data is normally distributed or a Mann-Whitney U test if data is not normally distributed.

If possible based on population size, concordance between groups of aPTT and anti-factor Xa activity will be assessed with a suitable (parametric or non-parametric) mixed effects statistical model. This approach is likely to yield more accurate information than crude correlation assessments that have been used in other studies, which have not taken into account repeated measures within patients. We will use repeated measures ANOVA and Tukey's test for multiple comparisons to analyze heparin administration in the two groups. With a mixed effects model, we will compare heparin dose in the two groups, while controlling for confounders, including the effect of time on the dose of heparin administered, and assuming an autoregressive covariance structure (the nature of the correlations between measurements for the same patient), as well as a random intercept to allow for some of the effect of potential unknown confounders.

If possible based on study size, markers of gastrointestinal bleeding, major bleeding, neurologic events, and thrombotic complications will be compared with a Chi-square test. Additionally, as able, adjusted logistic regression will be used to explore risk factors for complications. We will use intent-to-treat approach in our analyses. We will also use appropriate imputation methods and test the sensitivity of our results. No imputation is planned for missing primary outcomes data.

F Data Handling and Record Keeping

Data Collection and Methods

All questionnaire's performed will be collected and responses recorded.

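### Questionnaires collected from nurses on every shift are compared between arms by a plain Chi-square test, with no unit of analysis and no allowance for repeated forms on the same randomised patient

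*Combined protocol and SAP*

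**What the plan says.** The questionnaire is the first listed feasibility measure under the primary outcome (section B). Four places determine how its data arise and are analysed:

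- Section C, on clinical team training and feedback: "questionnaires for the nurses taking care of the study patients will be handed out by the research team on each nursing shift".
- Section C, Duration of Study: "Patients will be followed for 14 days of heparin therapy or until heparin has been discontinued", whichever comes first.
- Section F, Data Collection and Methods: "All questionnaire's performed will be collected and responses recorded".
- Section E: the questionnaires "will be analyzed with descriptive statistics and compared between the two groups using a Chi square test". The Synopsis agrees: "Chi Square and descriptive statistics used for questionnaire responses".

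Randomisation is by patient, 10 per arm (sections C and E). No section says whether the unit of analysis is the form, the nurse or the patient. None limits the number of forms per nurse or per patient.

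**The concern.** Forms about the same patient share an arm and a clinical course. A patient whose values stay out of range brings repeated rate changes, infusion holds and six-hourly draws. A stable patient moves to one draw each morning. Ratings of practicality may well follow that course. If they do, forms within a patient are correlated, and a test that counts each form as independent overstates the information in the comparison.

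The plan sees this problem elsewhere in the same section. For assay concordance it prefers a mixed model to "crude correlation assessments that have been used in other studies, which have not taken into account repeated measures within patients", and it models heparin dose with within-patient correlation. It makes no such provision for the questionnaires.

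The risk is that a chance difference between 10 and 10 patients is reported as a difference between nomograms, in a trial meant as the basis for a larger one. Confidence intervals computed from forms as if independent would be too narrow for the same reason.

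**Working it through.** The plan gives no figure to reproduce: the sample is one of convenience, no power analysis is planned, and no alpha or form count is stated.

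**Inputs from the documents.** 20 patients, 10 per arm; forms on each shift; at most 14 days of heparin. The Background section reports an earlier survey of 56 nurses on the existing aPTT nomogram, in which 55 (98.2%) "nurses felt the current dosing provided in the nomogram is feasible and 53 (94.6%) stated that they follow" its instructions exactly. I use 98.2% and 94.6% as favourable rates.

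**Assumptions not in the documents.** Two-sided alpha 5%; a further favourable rate of 90%; 5, 14 or 28 forms per patient (28 = 14 days × 2 shifts); latent-scale intraclass correlation (ICC) between patients of 0.05, 0.10 or 0.20; Pearson Chi-square without continuity correction; no true difference between arms.

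**Formula.** With m forms per patient and ICC ρ on the observed yes/no scale:

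- design effect D = 1 + (m − 1)ρ
- true error of a nominal 5% test ≈ 2[1 − Φ(1.96/√D)]

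The latent ICC is converted to the observed scale by ρ = [Φ₂(c, c) − P²]/[P(1 − P)], where c = Φ⁻¹(P) and Φ₂ is the bivariate normal probability with the latent correlation.

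**Worked example.** P = 94.6% and latent ICC 0.10 give ρ = 0.0267. With m = 28:

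- D = 1 + 27 × 0.0267 = 1.72
- 1.96/√1.72 = 1.494, so the true error is about 13.5%
- 280 forms per arm carry the information of 280/1.72 ≈ 163 independent forms

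Simulation of the same case also gives 13.5%.

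**Simulated type I error of the form-level Chi-square** (10,000 replicates; latent ICC 0.05 / 0.10 / 0.20):

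| Favourable | 5 forms | 14 forms | 28 forms |
|---|---|---|---|
| 90% | 5.9 / 6.6 / 8.6% | 7.2 / 10.7 / 16.9% | 11.2 / 16.5 / 26.3% |
| 94.6% | 4.6 / 5.4 / 6.2% | 6.6 / 8.9 / 12.9% | 9.3 / 13.5 / 22.4% |
| 98.2% | 1.1 / 1.2 / 1.5% | 5.5 / 5.9 / 8.8% | 6.2 / 8.8 / 14.0% |

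A repeat with 20,000 replicates agreed within about 1 percentage point. At 98.2% and 5 forms the test can hardly reject, since only 50 × 0.018 = 0.9 unfavourable forms are expected per arm. These figures assume equal form counts; unequal counts raise the error somewhat. They also use the latent scale, which gives the smaller values: an ICC of 0.10 on the observed scale with 28 forms gives D = 1 + 27 × 0.10 = 3.7 and an error of 30.8%.

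**Nurse effects alone** (56 nurses assumed, nurse ICC 0.2 to 0.5, no patient effect, 14 or 28 forms, 90% and 94.6% favourable). Error is 2-4% if nurses are balanced over the arms and about 5% if they are allocated at random. It is 6-16% if each patient has a team of six. Unless care is concentrated in small teams, the inflation therefore comes from patient clustering.

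**Patient as the unit.** A Welch t-test on the 10 and 10 patient percentages never exceeded 5%. At 14 to 28 forms it gave 3.9-4.9% (90% favourable), 3.3-4.8% (94.6%) and 1.8-3.3% (98.2%).

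**The case against.** The strongest reply is that this p-value decides nothing. The aim is to show that both nomograms can be implemented, not that one is rated better. Descriptive statistics are named first, and no alpha, threshold or progression rule uses the test. That is right, and it limits the harm. But the plan does specify a between-arm test on a primary feasibility measure, and its result would be read.

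Second, no evidence shows that the patient-level ICC exceeds zero. The earlier survey items rate the nomogram itself, so the nurse may be the main source of correlation, and nurses working in both arms make the test conservative. Several survey items were at or near 100%, where there is little to test. This stands as a reason not to claim a definite size. Yet the survey covered only the established aPTT nomogram, and the anti-Xa nomogram is new to these nurses.

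Third, 28 forms per patient needs two shifts a day, full return and the whole 14 days, which is a cap. That is fair: the 28-form column is an upper scenario for two shifts.

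Fourth, the plan does not say whether a continuity correction applies. With Yates' correction and 14 forms, the error is 5.2 / 7.7 / 13.0% at 90% favourable, 3.5 / 5.1 / 8.8% at 94.6% and 1.2 / 1.6 / 2.6% at 98.2%. At 5 forms it is 4% or less. At 28 forms and 94.6% it is still 6.2 / 9.5 / 17.4%. The correction shrinks the inflation without removing its cause.

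Finally, a patient-level analysis gives a patient with one form the same weight as a patient with 28. That is a real cost.

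**Conclusion.** The concern holds. Per-shift forms, all retained, are to be compared by a test that assumes independence, between arms of 10 randomised patients, and the plan neither names the unit nor handles repeats. Whether the error is inflated, and by how much, depends on form counts, ICC and response rates that the documents do not give. Under the assumptions above, the true error runs from below the nominal 5% (few forms, near-ceiling answers) to about 26% (28 forms, 90% favourable, latent ICC 0.20). The percentages by arm remain usable; the p-value and any form-level interval are what cannot be relied on. This should be corrected, but it does not threaten the trial. Confidence is medium, because the size rests on assumptions.

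**What to change.** In section E and the Synopsis, state that the patient is the unit of analysis for the questionnaires. For each item, compute each patient's percentage of favourable answers. Compare the 10 and 10 percentages by a t-test, Mann-Whitney test or permutation test in place of the form-level Chi-square. A permutation test should permute within LVAD type, since randomisation is stratified by it. Report the percentage favourable per arm with a patient-clustered interval, and the numbers of forms and of distinct nurses per arm. Reporting these descriptively with no test is a simpler and acceptable choice.

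Make sure that each form carries the patient's study ID and an anonymous nurse code. This has to be in place at collection, because clustering cannot be handled later without it. Use a model with patient and nurse effects only as a sensitivity analysis, if it converges; near-ceiling answers from 20 patients may not support it.

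The cost is two or three sentences and, if not already there, two fields on the form. The price is wider intervals, equal weight for patients with few and many forms, and a conservative test near ceiling: the t-test's size is about 2-3% at 98.2% favourable with 14 to 28 forms, and below 1% with 3 to 5.
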